Protocol for Comparative Efficacy of Self-directed & Therapist-assisted Telehealth Parent
Training Intervention for Children With ASD

NCT02721381

Based on last approval by MSU IRB on 4/6/2020

Risk to Human Subjects

a. Human Subjects Involvement, Characteristics, and Design

A total sample of 90 children with ASD between the ages 18-96 months and their primary caregivers will be recruited for this study. This sample size was determined to be adequate for maintaining adequate power for the proposed statistical analyses, while allowing for some attrition.

Inclusion Criteria for Families: To be eligible for participation, 1) the child must receive a DSM-V-informed clinical diagnosis of Autism Spectrum Disorder, based on the *Autism Diagnostic Observation Schedule* (ADOS). The diagnosis may be provisional for children under age 3 (typically listed as "at risk for ASD"). Children with this classification will be included as well. (2) The child must fall between the ages of 18 - 96 months at enrollment into the study, which will allow for data collection during the period of early intervention and early childhood special education programming. (3) The parent must understand spoken English as the training materials are presented in English.

Exclusion Criteria for Families: (1) Children with ASD who have a history of significant brain injury or known neurological condition in addition to a diagnosis of ASD, significant sensory impairment or major medical problems. These children and their families may require very specific adaptations to the treatment and thus the results will not be representative of children with ASD. This will be determined through review of medical records, diagnostic reports and parent interview. Criteria and data sources for identifying participants are outlined below.

Assignment to Study Group: Participating children and their primary caregivers will be assigned to one of three groups. Participants will be stratified by age (18-35 months; >36 months) and developmental quotient (DQ<55; DQ ≥55) at project enrollment, prior to being randomized. After stratification, participants will be randomly assigned to the one of the three groups using random permuted blocks of 6. This approach has been shown to yield groups that are closely balanced with regard to size and relevant pre-treatment characteristics. All pre-treatment assessments will be collected prior to randomization to prevent bias during testing based on knowledge of future group placement.

b. Sources of Materials

The sources of data for this study will include: (1) direct assessment of child functioning using standardized assessments; (2) completion of standardized questionnaires by parents; (3) written survey completion by parents; and (4) videotaped coding of treatment processes. All data will be used exclusively for research purposes. All surveys and interviews will use codes rather than subject names. Only the PI and primary research team members will have access to subject identities. Procedures to minimize risk of loss of confidentiality are presented below.

Child Measures: Child diagnostic testing will be conducted at pre-treatment. We will also examine specific child characteristics (cognitive ability level, language level, autism severity) that are predicted to be related to the impact of the parent-implemented interventions. We will administer the Autism Diagnostic Observation Scale, 2nd Edition (ADOS-2) to the child at pre-treatment. The ADOS-2 is a standardized protocol for observation of social and communicative behavior associated with a diagnosis of ASD that has been shown to have high reliability and discriminant validity. Recent longitudinal studies have demonstrated that diagnostic stability for children under age 3 is best when using DSM-IV based clinical judgment in conjunction with results from standardized diagnostic instruments, such as the ADOS. As in previous studies, this is the approach that will be used in the present study in order to determine a specific DSM-V diagnosis for each child. The PI has established research reliability on the ADOS. She will train the clinical research staff on these methods (as needed) and supervise all assessments. Child cognitive ability will be assessed using the Mullen Scales of Early Learning at T1. Child intentional communication with the parent will be scored from a parent-child interaction in the home at pre-treatment and post-treatment using weighted frequency of intentional communication. Language outcomes will be assessed at pre-treatment and follow-up using the

Mullen Scales of Early Learning, a parent report measure (the MacArthur-Bates Communicative Development Inventory) and the Vineland Adaptive Behavior Scales.

Parent Measures: Parents will complete the Parenting Sense of Competence Scale at pre-treatment, post-treatment, and follow-up to assess parent self-efficacy. Using the videotapes of the parent-child interaction in the home at pre-, post-treatment, and follow-up, the research team will assess parent use of the intervention strategies. Parents will also be asked to provide demographic information and complete the Parent Expectancies for Therapy Scale, a measure of treatment expectancy, the Computer-Email-Web Fluency Scale, a measure of computer/internet fluency, at pre-treatment, and the Parenting Stress Index, a measure of parenting stress at pre-treatment. Parents will be asked to complete the Treatment Evaluation Inventory, measure of treatment acceptability, at the conclusion of treatment. Parents will complete the Additional Services Form to monitor the type and number of hours per week of all non-study treatments once per month throughout study participation.

c. Potential Risks

There are no known serious health or psychological risks related to participation in this study. Procedures to minimize risk of loss of confidentiality are presented in the following section. In addition, there are legal limits to the confidentiality of information obtained during the research study. All information obtained from participants will be held confidential unless there is serious threat of harm to a child or to self or others. These limitations will be addressed in the consent forms. Collection of data from participants will include standardized child assessment measures, standard parent questionnaires regarding their child's development and behavior, standard parent questionnaires about their well-being and satisfaction with treatment, and videotape recordings. Precautions will be applied to all collected data from these activities, which will be stored in a private, secure and confidential location at MSU. All participants will be made aware of how collected data will be handled.

Adequacy of Protection Against Risks

a. Recruitment and Informed Consent

Primary caregivers of children with ASD will be recruited to participate in this study. Recruitment will be conducted through our ongoing contacts in Intermediate School District preschool special education programs and with clinicians at a number of sites in Lower Michigan. If a child appears to be eligible for the study, the clinician at that site will introduce the study to the family and present them with a brochure about the research project. In addition, a description of the study will be placed on the P.I.'s website which the public can access. Families who wish to participate will contact the project manager directly. The project manager will contact families to further explain the study, answer questions and schedule the first assessment session. The project manager will schedule an initial interview with the parents. At the beginning of that interview, the consent documents will be reviewed and written consent will be obtained from the parent. No child assent will be obtained because all children are expected to have significant cognitive and language delays that would prevent them from giving informed assent. Potential participants will be informed about the purpose and nature of the study and their rights as a participant. Written consent will be secured prior to the initiation of study participation. Participants will be assured of the maintenance of confidentiality and informed of their right to refuse to provide any data. Participants will be assured that data will only be reported in aggregate form without any individual identifying information. Parents will be compensated with \$25 for the pre-treatment, post-treatment, and follow-up assessment, totaling \$75. Each assessment period will consist of three to four hours of testing, involving direct child assessment, parent interview, and on-line data collection which may be completed across one to two visits. Applications for informed consent will be submitted to MSU's Human Research Protections Program. The nature of the proposed Research Plan is very similar to approved

studies currently being conducted by the P.I. As required, all amendments will be submitted for approval before being implemented. Annual project renewals will be submitted as required.

b. Protection Against Risks

1. Protection of Confidentiality: The current research proposes to collect both (a) personally identifying data (e.g., name, birth date, ethnicity, etc.) and (b) research data (e.g., interviews, diagnostic data, clinical assessment data, etc.). When connected only to a numeric identifier, the majority of the research data does not contain information that could identify a participant. When possible, standard protocols containing a numeric research identifier will be employed to separate personally identifying information from the research data. Video files will be coded with only the unique numeric identifier. The PI has had substantial experience ensuring the safety and confidentiality of video data. Personally identifying information will be stored in a single database that is located in the PI's lab. This database will be encrypted and have an access password that is only known to the PI and appropriate research members. Research data collected will be coded with a participant's unique identifier, or number and personally identifying data will not appear on any research data. All individuals working on the study will sign confidentiality agreements to never disclose any individual information regarding any aspect of the study. All data will only be reported in aggregate form without any identifying information.

2. Legal Limits of Confidentiality: There are legal limits to the confidentiality of information obtained in the data collection process. As a Licensed Psychologist, [name] is a mandated reporter of child maltreatment risk. Specifically, if direct evidence of child maltreatment is reported in a research interview and/or observed in one of the videotaped parent training sessions, the researcher will communicate any such concerns to the PI and it may be reported to Child Protective Services. The PI will evaluate any possible reportable content or event and will make the report, if she deems there to be significant risk to a child's safety and/or health. Similarly if there is direct evidence of imminent suicide, partner violence, or homicide risk expressed by a parent in a research interview or during training phone calls, researchers will be trained to document any concerns related to safety risk and communicate these immediately to [name] who will be on-call at all times. She will evaluate any potentially reportable content or event; consult with other experts at MSU, contact authorities as warranted, and make immediate follow-up calls to respondents who are acutely distressed. Given the characteristics of the subject population, the prevalence of child maltreatment and other concerns that require breach of confidentiality (e.g., suicidal risk) is not anticipated to be extremely high, but awareness of these issues will be maintained. Participants will be informed of these limits of confidentiality in the consent form. Any adverse events will be reported to the MSU Human Research Protections Program and the assigned Program Officer at the relevant NIH institute within one week of the occurrence, and summarized in the annual progress reports.

3. Other Risks: While not an adverse event, general discomfort may occur as participants are asked to discuss sensitive information. Efforts will be made to minimize potential discomfort associated with participating in any portion of this research. Consent forms will inform parents that they may discontinue their child's participation at any point in time. To minimize any potential discomfort or inconvenience associated with the research interviews and child assessments, such interviews and assessments will be scheduled at the participants' convenience in the family home. The intervention that will be used with the participants with autism is based on well-established principles of Applied Behavior Analysis and developmental psychology that have been used with autistic individuals for many years without resulting in any physical or emotional harm. Due to the behavioral difficulties exhibited by the target population, there is a potential risk of subjects becoming frustrated or bored during the training procedure or child assessments. Empirically documented behavioral management techniques will be used to address any tantrum behavior in the child participants. These techniques will include redirection

(i.e., trying to get the child interested in a positive behavior such as playing with a new toy when exhibiting negative behavior) and positive reinforcement for positive behavior (e.g., praise, access to desired materials). In some cases, extinction (i.e., ignoring the child's negative behavior) will be used if the two previous techniques are not effective. When using extinction, the parent will not ignore any self-injurious or dangerous behavior. If the child becomes too upset (unable to calm him or herself down within 10 minutes) or if the participant's parent becomes upset at his or her child's distress, parents will be encouraged to discontinue training.

Potential Benefits of the Proposed Research to the Subjects and Others

Parents will be provided with a report of their child's assessment results at pre-treatment and follow-up assessment. These reports will include the results of a comprehensive diagnostic evaluation. This report will only be shared with the parents, with our standard caveat that the purpose of the evaluation was as part of their participation in a research study and therefore should not necessarily be considered the equivalent of a clinical report. In our experience, parents usually find these reports to be quite helpful and many choose to share a copy with their child's service providers. Parents randomly assigned to the self-directed and therapist-assisted telehealth intervention groups will receive an internet-based parent training intervention that will be adapted from an evidence-based curriculum. Parents in the control group will be offered access to the self-directed telehealth intervention at completion of the study. There are no other direct anticipated benefits of participation in this study. There is, however, anticipated benefit of the knowledge gained from this study regarding parent-implemented interventions to improve outcomes for children with ASD and their families.

Importance of the Knowledge to be Gained

Knowledge gained from this research study will provide much needed information about ability to provide parent training for families with a child with ASD over the internet. Data available to date indicates great promise for parent training in terms of improving child outcomes and improving the quality of life for parents. Parent-delivered interventions can be implemented for relatively modest costs and provide services to a large number of families, in contrast to the high costs and limited availability of intensive child-directed services. While these parent-focused programs are not meant to replace intensive child-directed services for children with ASD, they appear to provide complimentary benefits and help to ameliorate the need for autism-specific services in areas where providers are in short supply. The provision of parent training over the internet has the potential to greatly increase the number of parents who can access these services, particularly in underserved areas where access to intervention providers is limited.

Statistical Analysis Plan

Overall Approach. The current study will use the Intention-to-Treat model (ITT) in the analysis of the primary aims. The ITT approach requires that all participants who are randomly assigned be compared on outcomes regardless of their adherence to treatment, reasons for withdrawal, or missing responses. Accordingly, we will include all participants in data analysis, follow up participants who withdraw from treatment, and impute missing data, as described below.

Missing Data. We will use the Expectation Maximization (EM) algorithm in SPSS to impute missing data for analyses that require complete data (e.g., Process Macro).

Preliminary analyses. To determine the comparability of groups on non-treatment variables after randomization, group differences will be examined for all T1 pre-treatment and descriptive variables. If significant group differences are detected for a given variable, and the variable of interest, then the variable will be used as a covariate in subsequent analyses as appropriate.

We will also examine age and DQ effects and identify whether treatment effects are moderated by either.

Aim 1: To examine the comparative efficacy of self-directed and therapist-assisted *ImPACT Online* on parent outcomes at post-treatment and the 3-month follow-up. To test our primary hypotheses for Aim 1, we will use multilevel modeling with restricted maximum likelihood estimation to examine the effect of group assignment on our primary and secondary parent outcomes. Time point (pre-treatment, post-treatment, follow-up) will be coded as a categorical variable. Change over time across groups will be estimated with the main effect of time, and between-group differences in change in outcomes will be estimated with the group by time interaction.

Aim 2: To examine the comparative efficacy of self-directed and therapist-assisted *ImPACT Online* on child outcomes at the 3-month follow-up. Three measures of verbal language will be collected at pre-treatment and follow-up. If child language measures are sufficiently correlated with each other ($r > .50$), we will create an equally weighted composite variable by z-scoring and summing the language measures. ANCOVA will be used to test for mean differences between the three conditions at follow-up. Pretest values will be included as covariates.

Aim 3: To examine whether pre-treatment parenting stress moderates the effects of *ImPACT Online* on parent fidelity and parent self-efficacy at post-treatment. Pre-treatment parenting stress will be included in the MLM models as a covariate. The pre-treatment parenting stress by time interaction will be used to determine whether pre-treatment parenting stress moderates change over time, irrespective of treatment group. The three-way interaction of pre-treatment parenting stress, group, and time will be used to examine whether the relationship between group assignment and change over time (i.e., group slopes) varied by pre-treatment parenting stress. A significant interaction will be followed up by simple slopes analyses.

Aim 4: To examine whether gains in parent fidelity (or parent self-efficacy) and child intentional communication at post-treatment mediate the effects of the *ImPACT Online* on child verbal language at the 3-month follow-up. We will conduct two serial mediation analyses using the PROCESS macro in SPSS to examine whether gains in parent fidelity (Mediator 1) and child intentional communication (Mediator 2) at post-treatment mediate the effect of *ImPACT Online* in child outcomes at follow-up. A second serial mediation analysis will be conducted to examine whether gains in parent self-efficacy (Mediator 1) and child intentional communication (Mediator 2) at post-treatment mediate the effect of *ImPACT Online* in child outcomes at follow-up.

Aim 5 (exploratory): To identify predictors of parent adherence to *ImPACT Online* for the two treatment groups. This exploratory aim will be addressed using a multiple regression approach in which level of therapist support (self-directed versus therapist assisted) and three individual-level factors (computer and internet fluency, expectancies of treatment, and treatment acceptability) serve as primary predictors of parent adherence. We will also examine sociodemographic variables as predictors as well.

Power Analysis. A series of power analyses were conducted using Borm, Fransen, & Lemmens⁸⁹ method for estimating sample size for analyses including a covariate. This approach takes into account the degree of association between the covariate and the outcome (r) by adjusting the required sample size required for an analysis without a covariate by $1 - r^2$ and then adding one extra participant per group. In our case, the covariate is the outcome variable as assessed at the pre-test. Analyses predicting parent fidelity (i.e., Aims 1 & 2) assumed a T1 to T2 correlation in fidelity of $r = .35$, and for self-efficacy, the T1 to T2 correlation was assumed to be $r = .75$. Across the aims involving parent fidelity we found that a sample size of 90 participants would provide 80% power to detect moderate to large effects of treatment condition (e.g., Cohen's $f = .32$). For parent self-efficacy a sample of 90 would provide 90%

power to detect moderately sized treatment effects (e.g., $f = .25$). For the child language variables we assumed a correlation between pretest and follow-up of approximately $r = .65$ for each of the three measures. Analyses predicting child language variables at follow-up controlling for pretest language scores (i.e., Aims 2 & 4) indicated that a sample size of 90 participants will have approximately 90% power to detect a moderate effect size ($f = .25$) for treatment condition.

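### The protocol says 90 families allow for some attrition, but at the stated 80% power for parent fidelity the plan's own method leaves essentially no reserve

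*Combined protocol and SAP*

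**What the plan says.** In Risk to Human Subjects, section a, the protocol fixes the recruited number: "A total sample of 90 children with ASD between the ages 18-96 months and their primary caregivers will be recruited for this study". The next sentence adds the claim at issue: "This sample size was determined to be adequate for maintaining adequate power for the proposed statistical analyses, while allowing for some attrition". No attrition rate, number of evaluable families or replacement rule is given there or elsewhere.

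Under Assignment to Study Group, families are "randomly assigned to the one of the three groups using random permuted blocks of 6". The allocation ratio is not stated.

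The Power Analysis at the end of the Statistical Analysis Plan allows for the pre-test covariate by "adjusting the required sample size required for an analysis without a covariate by $1 - r^2$ and then adding one extra participant per group". It assumes a correlation between T1 and T2 of .35 for fidelity and .75 for self-efficacy. Its results for the parent outcomes are:

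- Fidelity, f = .32: "Across the aims involving parent fidelity we found that a sample size of 90 participants would provide 80% power".
- Self-efficacy, f = .25: "For parent self-efficacy a sample of 90 would provide 90" per cent power.

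The Overall Approach and Missing Data paragraphs plan an intention-to-treat analysis of everyone randomised and continued follow-up of families who leave treatment. EM imputation is for analyses that need complete data. Aim 1 uses a multilevel model over three time points. None of this is linked to the sample size.

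**The concern.** The number recruited and the number entered in the power statements are the same. A sample can include an attrition allowance only if the power was worked out for fewer families than will be recruited, or if the stated power is visibly exceeded at the recruited number. The first is not the case, so the question is whether the second is.

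If it is not, the protocol claims a reserve that its own calculation lacks. The practical risk is in interpretation: after ordinary dropout, a null result on parent fidelity would be read against 80% power when the power actually available was lower.

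**Working it through.** **Inputs.** From the documents: 90 families, three groups, f = .32 and r = .35 with 80% power for fidelity, and f = .25 and r = .75 with 90% power for self-efficacy. Assumed: equal allocation (30 per group) and alpha .05 for the overall three-group F test, since neither is stated. The alpha is supported by the fact that it reproduces both stated powers. Alpha .025 would give 72.1% and 82.7%, and .10 would give 88.5% and 93.9%.

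**Method.** Without a covariate, power comes from the noncentral F distribution with 2 and N − 3 degrees of freedom and noncentrality N × f². The plan's adjustment is

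required total = N(no covariate) × (1 − r²) + 3.

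Run backwards, n analysed families are worth (n − 3)/(1 − r²) families without a covariate.

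**Step 1: reproduce the stated powers at 90.**

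- Fidelity: 1 − .35² = .8775; (90 − 3)/.8775 = 99.1; power 80.9% (stated 80%).
- Self-efficacy: 1 − .75² = .4375; (90 − 3)/.4375 = 198.9; power 89.0% (stated 90%).

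Fidelity reproduces. Self-efficacy is one point lower.

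**Step 2: families needed for the stated powers.**

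- Fidelity: 98 without a covariate; 98 × .8775 + 3 = 89.0. Worked per group, 33 × .8775 + 1 = 29.96, which rounds up to 30 per group, or exactly 90.
- Self-efficacy: 206 without a covariate; 206 × .4375 + 3 = 93.1. On the power curve the smallest whole number that reaches 90% is 93.

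**Step 3: power as outcome data are lost.** The documents give no loss rate, so a range is shown. A lost family is taken to contribute nothing.

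| Families with outcome data | Fidelity, f = .32 | Self-efficacy, f = .25 |
|---|---|---|
| 90 | 80.9% | 89.0% |
| 89 | 80.4% | 88.6% |
| 88 | 79.9% | 88.2% |
| 81 (10% loss) | 76.0% | 85.1% |
| 72 (20% loss) | 70.2% | 80.1% |

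**Step 4: sensitivity to the variant.** A direct ANCOVA calculation (N − 4 error degrees of freedom, noncentrality N × f²/(1 − r²)) gives 82.1% for fidelity at 90 and reaches 80% with 86 families. For self-efficacy it gives 89.4% at 90 and needs 92 for 90%. Dropping the extra participant per group gives minimum numbers of 86 and 90. No variant leaves a reserve for both outcomes at their stated powers, and the largest reserve for fidelity is four families (90 − 86).

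**The case against.** Four points can be made for the plan.

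- **The protocol promises adequate power, not the exact stated powers.** This stands for self-efficacy. If 80% counts as adequate, as it does for fidelity in the same paragraph, self-efficacy tolerates a 20% loss. It does not help fidelity, where 80% is the stated figure with all 90 and no lower level is called adequate.
- **Leaving treatment is not the same as losing outcome data.** The plan follows up families who withdraw, and the multilevel model keeps a family that misses only one later assessment. This also stands: the losses in the table are those for families with no usable outcome, and real losses of power may be smaller. However, the Power Analysis models neither feature, so neither can be the allowance that the protocol refers to. Imputing an outcome that was never observed does not restore the missing information.
- **A count in single families is too fine.** The powers are rounded, the effect sizes are given as examples, and the alpha is unstated. The count does move between one and four families with the variant, so it should be read as essentially none.
- **The decline is gradual.** The fidelity effect detectable with 80% power moves from f = .317 at 90 families to .335 at 81 and .357 at 72. That is a modest change, but it is not the zero cost that the wording suggests.

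A reader might infer that both parent powers fail once more than one family is lost. The documents do not support that. The self-efficacy gap is one percentage point with nobody lost, so it is a matter of rounding rather than attrition.

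**Conclusion.** The attrition statement is not supported for parent fidelity. The stated 80% needs 89 of the 90 families by the plan's method, or 86 by direct ANCOVA. Self-efficacy is at about 89% with all 90, so it has no reserve at 90%, but it keeps at least 80% down to 72 families.

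At 10% loss of outcome data, power is about 76% for fidelity and 85% for self-efficacy; at 20% loss, about 70% and 80%. These figures assume alpha .05, equal groups, an overall three-group test as a stand-in for the planned multilevel model, and no information from lost families.

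A reader might go further and conclude that the trial is underpowered for its parent outcomes or must enrol more. Neither follows. The fidelity figure is right for 90 families with data, the documents give no attrition rate, and the planned follow-up and model may recover some power. What is wrong is the description of the sample, and it is cheap to correct.

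**What to change.** In Risk to Human Subjects, section a, remove the attrition phrase, or qualify it to say which outcome and power level it applies to.

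In the Power Analysis, for parent fidelity and parent self-efficacy only:

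- say that the figures assume 90 families with outcome data;
- give self-efficacy as about 89%;
- state the alpha;
- add power at a stated expected retention, for example about 76% and 85% with 81 families, or about 70% and 80% with 72;
- note that these figures treat lost families as contributing no outcome data, so follow-up of families who withdraw and partial data in the multilevel model may do somewhat better.

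Do not extend this wording to child language. The approximately 90% stated there (r = .65, f = .25) comes out at about 78% with 90 families by the same method: 1 − .65² = .5775, and (90 − 3)/.5775 = 150.6. That figure needs its own correction, and a general sentence about 90 families with data would appear to confirm it.

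The cost is a few reworded sentences and a less favourable power statement. Conduct and enrolment do not change.

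### One disclosed block size of 6, with no stated concealment, makes testing before randomization only an incomplete protection against foreknowledge

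*Combined protocol and SAP*

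**What the plan says.** The protocol's Assignment to Study Group paragraph sets out three arms ("Participating children and their primary caregivers will be assigned to one of three groups"), four strata ("Participants will be stratified by age (18-35 months; >36 months) and developmental quotient (DQ<55; DQ ≥55) at project enrollment, prior to being randomized") and one block size ("participants will be randomly assigned to the one of the three groups using random permuted blocks of 6"). It gives one protection against foreknowledge: "All pre-treatment assessments will be collected prior to randomization to prevent bias during testing based on knowledge of future group placement".

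Other sections bear on who could know what, and when:

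- **Source of DQ.** Child Measures says "Child cognitive ability will be assessed using the Mullen Scales of Early Learning at T1". No other cognitive test is described, so the Mullen is presumably the source of the DQ stratum, although the protocol does not say so.
- **Who tests.** Of the PI, Child Measures says "She will train the clinical research staff on these methods (as needed) and supervise all assessments".
- **Who rates parent fidelity.** Parent Measures says that from home videotapes "the research team will assess parent use of the intervention strategies".
- **Who schedules.** Recruitment and Informed Consent says "The project manager will contact families to further explain the study, answer questions and schedule the first assessment session".
- **The arms.** The section on potential benefits describes self-directed telehealth, therapist-assisted telehealth, and a control group offered the self-directed program after the study. Families and treating staff can tell these apart.

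The documents do not say who generates or holds the sequence, how it is concealed, whether the block size is withheld from staff, or whether testers and video coders are masked.

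**The concern.** Testing before randomization keeps an assignment unknown only if it cannot be worked out beforehand. With three distinguishable arms and a block size printed in the protocol, anyone who tracks a stratum can see the end of each block coming. Under equal allocation a block of 6 holds two of each arm, so the sixth placement is always fixed by the first five, and the fifth sometimes by the first four.

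Foreknowledge could affect how the remaining baseline measures are taken, or which of two ready families is randomized next. Baseline values are the covariates in the Aim 2 ANCOVA and the first time point in the Aim 1 multilevel model. An arm-related distortion at baseline would therefore enter the treatment comparisons.

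**Working it through.** The plan states no predictability figure, so there is none to reproduce.

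**Inputs.** From the protocol: 3 arms, blocks of 6, 2 × 2 = 4 strata, 90 families. Assumed: equal allocation (2:2:2 per block; the ratio is not stated), and an observer who knows the block size, the stratum and all earlier assignments in it.

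**1. One complete block.** There are 6!/(2!·2!·2!) = 90 equally likely orders.

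- Certain placement: the sixth always. The fifth is certain when the last two are the same arm: 3 × 6 = 18 of 90 orders = 0.20. Positions 1-4 never. Mean = (0.20 + 1)/6 = 20.0%.
- At least one arm ruled out, by position: 0, 0, 0.2, 0.6, 1, 1. Mean = 2.8/6 = 46.7%.
- Control versus active known, by position: 0, 0, 1/15, 3/15, 7/15, 15/15. Mean = (26/15)/6 = 28.9%.
- Best guess correct, by position: 0.333, 0.400, 0.500, 0.533, 0.600, 1. Mean = 3.367/6 = 56.1%, against 33.3% by chance.

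**2. Ninety families in four strata.** Last blocks are usually incomplete. If 0 to 5 leftover families are equally likely in each stratum, the average is 2.5, or 10 over four strata, which leaves 80 in complete blocks.

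- Certain placements = (80/6) × 1.2 + 4 × (1/6) × 0.2 = 16.0 + 0.13 = 16.1, and 16.1/90 = 17.9%.
- A 2,000-run simulation agrees: 17.9% certain, 43.5% with an arm ruled out and 54.6% guessed correctly. Unequal strata (20/10/40/30%) give nearly the same.
- With exactly 22 families per stratum (three full blocks plus four), the figure is 3 × 1.2/22 = 16.4% (simulated 16.3%).

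The range is thus about 16-18%: 0.163 × 90 = 14.7 to 0.179 × 90 = 16.1 families.

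**3. Before DQ is scored.** With only age known, the family could fall in either of two strata. Placement is certain only if both strata are at a determined position and point to the same arm: 0.20 × 0.20 × 1/3 = 1.3%. The simulation, with incomplete blocks, gives 1.2% (about 1 of 90), 12.3% with an arm ruled out, and about 51% guessed correctly.

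**4. Effect of varying the block size.** Simulated with 22 families per stratum and an observer who knows the set of sizes but not their order:

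| Block sizes | Certain | Best guess correct |
|---|---|---|
| 6 only | 16.3% | 53.9% |
| 3, 6 | 7.6% | 56.3% |
| 6, 9 | 4.6% | 52.6% |
| 3, 6, 9 | 3.0% | 53.8% |
| 6, 9, 12 | 2.1% | 51.2% |

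Varying the size removes most of the certainty but little of the guessing.

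**The case against.** The strongest reply is one of timing. Explaining the study and scheduling the first visit happen before the child is tested. If DQ comes from the Mullen at T1, the stratum is then unknown and certainty is about 1%. The review of medical records and diagnostic reports in the inclusion and exclusion criteria serves the exclusions; nothing shows that it yields a DQ. This stands, and it moves the exposure to a later window. The protocol fixes no order of measures and allows one to two visits, so some measures may follow the Mullen. After testing, the stratum is known while the family waits to be randomized.

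A second reply is that no text shows testers seeing past assignments. Site clinicians introduce the study, families contact the project manager, and clinical research staff are trained for the assessments. That also stands: staff knowledge is an assumption here. A reader might infer an open-label trial in which one team recruits, schedules and tests. The documents do not use that term, and they do not describe such a single team.

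Third, the route to bias is narrower than it may seem. Several baseline measures are completed by parents. In the Aim 2 ANCOVA a baseline shift is scaled by the covariate slope (the power analysis assumes a correlation of about .65). If fidelity videos are coded after randomization, the issue for that outcome is masking of coders, not the block size. No bias in an effect estimate can be computed from the documents.

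**Conclusion.** The concern holds in a limited form. A single disclosed block size, distinguishable arms and no described concealment leave testing first as an incomplete safeguard. With the stratum and history known, about 16-18% of placements (15-16 of 90) are certain; before DQ is scored, about 1%. The exposed steps are baseline measures taken after the Mullen and the order in which ready families are randomized.

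Two stronger readings are not supported. A reader might take the complete-block figure of 20%, or 18 of 90, as the trial's exposure, but that requires every block to fill and the stratum to be known throughout. A reader might also conclude that staff can generally deduce placements, so that testing first protects nothing. Yet more than 80% of placements are not certain even with full knowledge, and testing first still hides the actual assignment.

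The figures rest on 2:2:2 blocks and on staff knowing the block size, the stratum and earlier assignments. The documents neither confirm nor exclude that knowledge. The change is worth making because it is cheap, not because bias has been shown.

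**What to change.** In Assignment to Study Group:

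- Replace the single block size with sizes varied at random among multiples of three within each stratum (for example 3, 6 and 9, or 6, 9 and 12). Keep the sizes out of documents that staff use. Certain placements fall to about 2-3%. The pair 3 and 6 is a poor choice: 7.6% remain certain and guessing is slightly easier than with 6 alone.
- Because guessing stays at about 51-54%, name an existing team member who neither recruits nor tests to hold the list. That person releases each assignment only after the family's baseline data are locked.
- Keep testers unaware of past allocations where feasible, and state whether testers and video coders are masked.

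The cost is a new computer-generated list and a few sentences. The downside is slightly larger possible imbalance: within an unfinished block two arms can differ by up to one third of the block size, which is 2 for a block of 6, 3 for 9 and 4 for 12.
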